4.3 ALTERNATIVE PRIMARY ENDPOINT

To address the possibility of missing data arising from COVID-19, this SAP incorporates the ability to determine a new definition for the primary endpoint based on a fully blinded assessment for missing data. Section 9.2 of the SAP defines the decision rules, data handling, and analyses for the alternative definition of the primary endpoint. In general, the amount of missing 6MWD data potentially due to the COVID-19 pandemic interfering with onsite measurements will define whether adaptation is necessary. At the conclusion of the study, a blinded analysis will be performed to assess the extent of missing primary efficacy endpoint data (ie, 6MWD data). If the absence of 6MWD data in the Treatment Period, combined across subjects, treatment periods, and key visits (Baseline and Study Week 12) to be used for the final primary endpoint analysis would likely lead to an underpowered study or yield indeterminate results, an alternative primary endpoint will be used for the final primary endpoint analysis (see Section 9.2 for decision rules). The 6MWD is to be used as the primary efficacy endpoint for this study, except in the case where onsite measurements for the 6MWD are not practically available, and will occur independently of Adaptation 1 (ie, for either the Original Crossover Design or the Contingent Parallel Design).

4.4 FINAL ANALYSIS

The final analysis is planned after all subjects have completed treatment or withdrawn from the study, the study database is locked, and the randomization codes have been revealed. All statistical analyses will be performed by the Sponsor's biostatistics department personnel (or appropriate designees) using SAS[®], Version 9.4 (or higher) or other validated software.

5 SAMPLE SIZE CONSIDERATIONS

5.1 PLANNED STUDY

The **Original Crossover Design** is a 2x2 crossover study designed to have 90% power to detect a placebo-corrected mean change from baseline difference of 30 meters, assuming that the

standard deviation of differences is 85 meters² and using a 2-group t-test with a 0.01 2-sided significance level, with a sample size of 124 subjects (62 in each sequence group). To account for a discontinuation rate of approximately 10%, the total sample size will be approximately 136 subjects.

The **Contingent Parallel Design** is a parallel-group study designed to use an allocation ratio of 1:1 between inhaled treprostinil and placebo, with a sample size of 266 subjects (133 per treatment) that would provide at least 90% power at a significance level of 0.05 (2-sided hypothesis) to detect a 30 meter between-treatment difference in the change from baseline in 6MWD, assuming a standard deviation of 75 meters. To account for a discontinuation rate of approximately 15%, the total sample size will be approximately 314 subjects. Should there be a switch to the Contingent Parallel Design, the analysis plan described in Appendix 12.4 will be followed.

5.2 [REDACTED]

[REDACTED]

² Note. Due to the smaller sample size expected for the crossover design a more conservative standard deviation of the difference (85 meters) was assumed (compared to 75 meters for a parallel design).

assignment. All safety analyses will be performed on this Safety Population, unless otherwise specified.

A summary table presenting the number and percentages of subjects for each analysis population will be presented by treatment group. Subjects who are excluded from any analysis population will be listed with reason for exclusion. The Sponsor must approve this list before treatment is unblinded and thus before performing final analyses.

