#### 10.2 SAMPLE SIZE

This is an adaptive design study that will be initiated as a crossover study (the **Original Crossover Design**). However, due to the uncertainty of clinical benefit with inhaled treprostinil exposure in PH-COPD subjects and the ongoing COVID-19 pandemic, there is a possibility of treatment discontinuations and/or missing data due to COVID-19 impeding onsite visits, which may render estimates for efficacy outcomes inefficient or biased, thus an automatic switch to the **Contingent Parallel Design** or an alternative primary endpoint that has been incorporated in this study protocol. The protocol specifies the algorithm to seamlessly transition to a parallel-group design (**Contingent Parallel Design**) if the degree of missing data subsequent to subject treatment crossover is not tolerable for primary analysis.

Similarly, this protocol specifies the algorithm to switch the primary endpoints to measurements conducted remotely if the COVID-19 pandemic prevents onsite visits and data collection for the intended primary endpoint data. Evaluations of missing data will be performed in a blinded fashion at the conclusion of the study, irrespective of actual efficacy outcomes and any information regarding efficacy outcomes prior to crossover and, as such, will not impact the Type I error rate (FDA Guidance 2019). Section 10.2.1 presents the adaptation procedures to be employed for this protocol.

The **Original Crossover Design** is a 2x2 crossover study designed to have 90% power to detect a placebo-corrected mean change from baseline difference of 30 meters, assuming that the standard deviation of differences is 85 meters and using a 2-group t-test with a 0.01 two-sided significance level, with a sample size of 124 subjects (62 in each sequence group). To account for a discontinuation rate of approximately 10%, the total sample size will be approximately 136 subjects.

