Based on published data using actigraphy as an outcome measure in studies conducted in the pulmonary hypertension population (Gonzalez-Saiz 2018; Nathan 2020), reasonable statistical power (80%; 2-sided alpha of 0.05) can be assumed for approximately 90 evaluable subjects when the observed improvement is in excess of 6%-8% for overall activity or 20-25% or greater for moderate to vigorous activity. Nathan (2019) provides that the clinically meaningful difference observed in their study was 5% to 10% for overall activity and 20% for MVPA, with a clinically meaningful difference range in studies of COPD patients from 11% to 29%.

The Contingent Parallel Design is a parallel-group study designed to use an allocation ratio of 1:1 between inhaled treprostinil and placebo, with a sample size of 266 subjects (133 per treatment) that would provide at least 90% power at a significance level of 0.05 (2-sided hypothesis) to detect a 30-meter between-treatment difference in the change from baseline in 6MWD, assuming a standard deviation of 75 meters. To account for a discontinuation rate of approximately 15%, the total sample size will be approximately 314 subjects.

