7 GENERAL CONSIDERATIONS FOR DATA ANALYSES

Given the crossover design utilized for this study, efficacy and safety summary tables will follow the general format that baseline and post-baseline data will be presented by the assigned treatment condition when those data are observed during the treatment period. Treatments will be labeled as “Treprostinil” and “Placebo” to correspond with the assigned treatment condition.

Any efficacy and safety data that are collected during the washout period between Periods 1 and 2 will be presented for the assigned treatment condition from Period 1. Any follow-up data collected after Period 2, while on this study, will be assigned to Period 2. Subjects who are not retained will not be replaced during the study.

For continuous variables, the summary statistics will include the mean, standard deviation, median, lower quartile, upper quartile, minimum, and maximum. Statistics will be expressed using the level of precision in which the variable was collected. For discrete variables, summaries will include the frequency and percent in each category. Whenever practical, categories of discrete variables will be ordered and labeled as they appear in the case report form (CRF), and all categories represented on the CRF will be included in summaries, even when they do not apply to any patients in the study.

For data collected on a fixed schedule, the nominal time point will be used for summarization. Evaluations from Unscheduled Visits are to be mapped to Scheduled Visits to the extent possible per the protocol-specified windows. Repeat or redundant observations within an assessment window and observations that do not fall within any predefined assessment window will be excluded from summaries. If an evaluation is repeated, such as to confirm an observed aberrant laboratory value, the analyses will use the later value if within the protocol-specified window.

Unless otherwise specified, all final statistical tests will be 2-sided at alpha level 0.05 if the interim analysis is not conducted, and 0.022, if conducted. All tables will be presented in landscape format. For practical reasons, the point size may be reduced to (but not less than) 7 point for tables that contain too much information to fit into a single page. SAS[®] version 9.4 or higher will be used. The Sponsor's Biostatistics Department will analyze the efficacy and safety data.

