7.1 BASELINE

Given the crossover design utilized for this study, Periods 1 and 2 each have a different baseline for efficacy measurements: Period 1: Day 1 and Period 2: Week 14. With the exception of actigraphy measurements, the baseline value will be defined as the non-missing value immediately prior to dosing with study drug for Period 1: Day 1 and Period 2: Week 14. The baseline period for actigraphy measurements will be the last 7 days during the washout period prior to the day of dosing on Day 1 and Week 14. In the event that the washout period is less than 7 days then only the non-dosing days will be used to derive a baseline average.

For safety evaluations, the baseline will be defined as the last evaluation closest, but prior to, the first dose of study drug during the low dose run-in period.

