7.4 COVARIATES

Efficacy analyses will include the assigned treatment sequence and period order as covariates. Change from baseline analyses will include the baseline measurement as a continuous covariate.

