9.1.2 Primary Efficacy Analysis Data

The primary efficacy analysis will be based on all available measurements of the 6MWD for the FAS as observed in the study, with the exception that for subjects whose 6MWD measures at Week 6 or Week 12 of either Period are missing due to death or being too ill to perform 6MWT, the missing values will be imputed as the worst possible score (0 meter) and change-from-baseline scores calculated. For missing data due to any other reason, the missing value will not be imputed.

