9.1.3 Primary Efficacy Analysis

Descriptive statistics showing the raw values and changes from baseline for the 6MWD will be presented for each scheduled visit by treatment. Additionally, boxplots presenting the raw values and changes from baseline for each visit for the 6MWD may be presented.

A mixed-effect model for repeated measures (MMRM) will be used to estimate the treatment effect. The magnitude of treatment effect will be compared between the 2 treatments across the 12-week treatment periods, and the test of the Week 12 change from baseline and difference between treatments will be produced using contrasts.

[REDACTED]

- [REDACTED]
- [REDACTED]
- [REDACTED]
- [REDACTED]
- [REDACTED]
- [REDACTED]
- [REDACTED]

[REDACTED]

[REDACTED]

[REDACTED]

- [REDACTED]
- [REDACTED]
- [REDACTED]
- [REDACTED]
- [REDACTED]
- [REDACTED]

Least square means for baseline adjusted 6MWD for each treatment group, difference of LS means between treatment groups with the associated p-value, and 95% CIs for each treatment LS mean and the difference in LS means will be summarized and presented.

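### Does ranking 85 m against 75 m in SAP 5.1 footnote 2 undermine the crossover sample size or call for a different baseline covariate?

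*SAP*

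**What the plan says.** Protocol 10.2 and SAP 5.1 size the crossover design for 90% power at 30 m, "assuming that the standard deviation of differences is 85 meters and using a 2-group t-test with a 0.01 two-sided significance level", with 124 subjects (62 per sequence). The Contingent Parallel Design uses 133 per arm "to detect a 30-meter between-treatment difference in the change from baseline in 6MWD, assuming a standard deviation of 75 meters", at two-sided 0.05. Footnote 2 to SAP 5.1 links the two SDs. It gives the smaller expected sample size as its reason and says "a more conservative standard deviation of the difference (85 meters) was assumed (compared to 75 meters for a parallel design").

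The final test is less strict than the sizing test. SAP 7 states that "all final statistical tests will be 2-sided at alpha level 0.05 if the interim analysis is not conducted, and 0.022, if conducted".

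On the model, SAP 7.1 says "Periods 1 and 2 each have a different baseline for efficacy measurements: Period 1: Day 1 and Period 2: Week 14", SAP 7.4 says "Change from baseline analyses will include the baseline measurement as a continuous covariate", and SAP 9.1.3 says "A mixed-effect model for repeated measures (MMRM) will be used to estimate the treatment effect". The model terms in 9.1.3 are redacted, as is SAP 5.2. For walks missing because of death or illness, SAP 9.1.2 says "the missing values will be imputed as the worst possible score (0 meter) and change-from-baseline scores calculated". SAP 9.2.1 derives its 65% data-presence rule from a floor of about 88 evaluable subjects (90% power, two-sided 0.05).

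**The concern.** A larger SD looks more cautious than a smaller one only if both measure the same thing, and here they do not. If the two period changes were uncorrelated, a change SD of 75 m would imply an SD of differences of 106 m. On that view 85 m would be optimistic. One number with no visible source would then set both the sample size and the rule that decides which primary endpoint is tested. The footnote also does not say whether 85 m allows for the 0 m values of SAP 9.1.2.

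A second worry follows from the covariate text. If the redacted model has one slope on the own-period baseline, that slope must serve both differences between subjects and differences within a subject. In a crossover this can waste precision that a split into subject mean and period deviation would recover from data already collected.

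**Working it through.** **Reproducing the plan (noncentral t).** In a 2x2 crossover the two sequence groups differ by 2 × 30 = 60 m in the mean period difference.

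- Crossover, 62 per sequence, SD 85 m, two-sided 0.01: power 90.3%.
- Parallel, 133 per arm, 30 m, SD 75 m, two-sided 0.05: power 90.1%.
- Floor of 88 subjects, SD 85 m, two-sided 0.05: power 90.6%. The 65% rule matches it: 0.65 × 136 = 88.4.
- Reading 85 m as the SD of one change in a parallel comparison gives N = 478, and as a root mean square error N = 244. Neither fits the stated 124.

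So 85 m is the SD of a within-subject difference of two changes, and 75 m is the SD of one change.

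**Common scale.** SD of differences = 75 × √(2(1 − ρ)), where ρ is the correlation between a subject's two period changes (not given in the documents).

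- Break-even with 85 m: ρ = 1 − 85²/(2 × 75²) = 0.358.
- ρ = 0.5 gives 75.0 m, and 85 m is then cautious.
- ρ = 0 gives 106.1 m with no baseline adjustment.

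**How much 85 m matters.**

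| SD of differences | N=124, 0.01 | N=124, 0.022 | N=124, 0.05 | N=88, 0.05 |
|---|---|---|---|---|
| 85 m | 90.3% | 94.5% | 97.4% | 90.6% |
| 95 m | 81.4% | 88.3% | 93.7% | 83.4% |
| 106.1 m | 70.2% | 79.5% | 87.8% | 74.7% |

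Solving for 90% power at N = 124 gives an SD of 102 m at 0.05 (ρ about 0.07) and 92 m at 0.022 (ρ about 0.24). At N = 88 and 0.05 the limit is about 86 m.

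**Baseline covariate.** Assume equal correlation among the four walks (so ρ = 0) and a change SD of 75 m. The within-subject SD of one walk is then 75/√2 = 53.0 m. With slope b on own-period baseline, the adjusted difference has SD 75 × √(1 + b²).

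- No covariate (b = 1): 106.1 m.
- One own-period slope: for an assumed between-subject SD of 60 to 120 m, b is 0.506 to 0.824 and the SD is 84.1 to 97.2 m. Power at N = 124 and 0.05 is 97.6% to 92.7%.
- Split baseline (within-subject b = 0): 75.0 m, power 99.3%.

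**Price under carryover.** Let a residual effect from active treatment in Period 1 be L14 at Week 14 and L25 at Week 25. The expected estimate is 30 − (L25 − b × L14)/2.

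- Lasting, 10 m at both visits: split 30 − 5 = 25 m. Single slope with b = 0.657 (between-subject SD 80 m): 30 − 5 × 0.343 = 28.3 m.
- Week 14 only, 10 m: split 30 m; single slope 30 + 5 × 0.657 = 33.3 m.

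Simulation gave 25.0 and 28.2 m in the first case, and 30.1 and 33.5 m in the second. The carryover test in SAP 9.1.4.2 compares sums of the two changes by sequence. Their expected difference is L25 − L14, which is zero for lasting carryover of constant size. The test cannot see the carryover that harms the split.

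**The case for a change.** The strongest case for acting has three parts.

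First, the footnote's reason is not a reason: an expected sample size does not determine an SD. That stands, and so does the absence of a correlation or source in the readable text. But SAP 5.2 is redacted, and nothing shows that 85 m is wrong.

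Second, the 88-subject floor is already at 0.05 and has almost no margin. That also stands. It binds only if about a third of the walk data are missing. At 95 m it still gives 83%, above the 80% minimum that SAP 12.4.5 accepts for the same rule in the parallel design. The 75% figure belongs to an analysis with no baseline adjustment, which is not the one planned.

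Third, the 0 m rule can inflate the SD. If 85 m leaves those values out, and if 1% or 3% of walks per period are set to zero with a mean baseline of 250 to 350 m (all assumptions), the unadjusted SD becomes 92–99 m or 105–122 m. Power at N = 124 is then 91–94% or 75–86% at 0.05, and 85–90% or 64–78% at 0.022. This is the most serious scenario. It depends on an exclusion that the documents do not state, and a sentence in the footnote would not add a subject.

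For the split baseline, the precision gain is real under the assumed covariance. It shrinks towards nothing when subjects differ little at baseline. At ρ = 0.36 in complete data, one own-period slope already gave 60–78 m in simulation, better than 85 m. Other readable text (SAP 9.4.1, 9.4.2 and 12.4.5) refers to an average baseline, so the redacted model may not be the one criticized.

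**Conclusion.** No change to the plan follows.

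The footnote is a slip of wording. It compares unlike SDs, and its claim is true only for ρ above about 0.36. Correcting it would alter no sample size, test or threshold: 124, 133 per arm and 88 all reproduce. It would be overstated to say that adequate power at N = 124 depends on 85 m being exact. Sizing at 0.01 and testing at 0.05 or 0.022 leaves room up to about 102 m or 92 m. The 88-subject floor lacks that room, but the documents offer no better SD from which to move it.

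The split baseline is a fair trade-off, not a correction. Under the assumed equal correlation it reduces the SD from 84–97 m to 75 m. In exchange, 10 m of lasting carryover removes about 5 m of a 30 m effect, against about 2 m with one slope. Washout 2 lasts only 7 to 14 days, and the planned carryover test cannot detect that pattern. The split also makes Week 14, measured after Period 1 treatment, a covariate for the Period 1 outcome. Keeping a single-slope model, if that is what the redacted text holds, is a defensible choice.

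These conclusions rest on assumed correlations, between-subject SDs, zero-walk shares and carryover sizes, because the readable documents give none of them.

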7 GENERAL CONSIDERATIONS FOR DATA ANALYSES

Given the crossover design utilized for this study, efficacy and safety summary tables will follow the general format that baseline and post-baseline data will be presented by the assigned treatment condition when those data are observed during the treatment period. Treatments will be labeled as “Treprostinil” and “Placebo” to correspond with the assigned treatment condition.

Any efficacy and safety data that are collected during the washout period between Periods 1 and 2 will be presented for the assigned treatment condition from Period 1. Any follow-up data collected after Period 2, while on this study, will be assigned to Period 2. Subjects who are not retained will not be replaced during the study.

For continuous variables, the summary statistics will include the mean, standard deviation, median, lower quartile, upper quartile, minimum, and maximum. Statistics will be expressed using the level of precision in which the variable was collected. For discrete variables, summaries will include the frequency and percent in each category. Whenever practical, categories of discrete variables will be ordered and labeled as they appear in the case report form (CRF), and all categories represented on the CRF will be included in summaries, even when they do not apply to any patients in the study.

For data collected on a fixed schedule, the nominal time point will be used for summarization. Evaluations from Unscheduled Visits are to be mapped to Scheduled Visits to the extent possible per the protocol-specified windows. Repeat or redundant observations within an assessment window and observations that do not fall within any predefined assessment window will be excluded from summaries. If an evaluation is repeated, such as to confirm an observed aberrant laboratory value, the analyses will use the later value if within the protocol-specified window.

Unless otherwise specified, all final statistical tests will be 2-sided at alpha level 0.05 if the interim analysis is not conducted, and 0.022, if conducted. All tables will be presented in landscape format. For practical reasons, the point size may be reduced to (but not less than) 7 point for tables that contain too much information to fit into a single page. SAS[®] version 9.4 or higher will be used. The Sponsor's Biostatistics Department will analyze the efficacy and safety data.

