Weekly Contact n	X	X	X	X	X	X	X	X	X	X	
QOL°				X u	X	X		Xu	X	X	X
PGA z				X	X	X		Xu	X	X	X
Subject Eligibility	X u	X		X u							
Pre-Baseline Review Form p		X									
Randomization q				X							
Drug/Device Accountability x		X			X	X			X	X	X

Can de Duo e de mas a	Screening Period a		Washout Period a	Treatment Period 1			Washout Period a	7			
Study Procedures a	Screening Visit 1	Screening Visit 2	Washout 1	Baseline Visit	Week 6 Visit	Week 12 Visit	Washout 2	Baseline Visit	Week 19 Visit	Week 25 Visit	Early Termination
Study Week	-9 to -3	-2	-1	1	6	12	13	14	19	25	N/A
Study Day	-63 to -22	-8 (or -4)	-7 to -1 a	1	42±3	84±3	85 to 91 a	92±3	133±3	175±3	N/A
Site Visit	X	X	N/A	X	X	X	N/A	X	X	X	X

6MWT, 6-Minute Walk Test; AE, adverse event; CT, computed tomography; DLCO, diffusion capacity for carbon monoxide; DNA, deoxyribonucleic acid; ECG, electrocardiogram; eCRF, electronic Case Report Form; ET, early termination; FEV1, forced expiratory volume in 1 second; FVC, forced vital capacity; HR, heart rate; N/A, not applicable; NT-proBNP, N-Terminal pro-brain natriuretic peptide; PFT, pulmonary function test; PGA, patient global assessment; QOL, quality of life; RHC, right heart catheterization; RNA, ribonucleic acid; SAE, serious adverse event; SGRQ, St. George's Respiratory Questionnaire; SpO2, saturation peripheral capillary oxygenation; TLC, total lung capacity; UCSD SOBQ, University of California San Diego Shortness of Breath Questionnaire

- a Sites may schedule non-invasive screening assessments, RHC, and study drug start on different days to facilitate scheduling. However, study drug exposure in the Screening Period must be for a minimum of 14 days (maximum of 18 days) and washout must be for a minimum of 7 days (maximum 14 days). If deemed necessary, per the clinical judgement of the site staff or Investigator, subjects may be asked to return to the study site for an unscheduled visit to assess their status. This visit may require blood draws, vital signs, and/or review of concomitant medications. Any assessments performed at an unscheduled visit should be recorded in the source documents and reported in the appropriate eCRF pages.

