#### 7 EXPERIMENTAL PROCEDURES

The allowable window for each study visit will be  $\pm 3$  days; however, where specified, the minimum Treatment or Washout Period must be adhered. Refer to Section 3.2 for the Overall Schedule of Times and Events.

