### 15.6 GUIDELINES AND DEFINITIONS FOR RECORDING ADVERSE EVENTS

The Investigator or a designated member of their staff will probe each subject for any AEs that may have occurred. The Investigator should always ask the same question when conducting the verbal probe in order to ensure uniformity between subjects. The Investigator should ask:

"How are you doing (feeling)?"

Based on the subject's response to this question, the Investigator should ask additional questions relevant to the specific complaint such as:

"How severe is/was the symptom?"

"How often did the symptom occur?"

"How long did the symptom last?"

It is the Investigator's responsibility to review the results of all diagnostic and laboratory tests as they become available and ascertain if there is a clinically significant change from baseline. If the results are determined to be a clinically significant change from baseline, this should be reported as an AE. The Investigator may repeat the diagnostic procedure or laboratory test or request additional tests to verify the results of the original tests. When possible, a diagnosis associated with the abnormality should be used as the reported AE.

Using provided definitions, the Investigator will then:

(1) rate the intensity and seriousness of the AE, (2) estimate the causality of the AE to study drug, and (3) note actions taken to counteract the AE.

Definitions of Intensity, Seriousness, Causality, Action Taken, and Outcome

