10.5 CLINICAL LABORATORY EVALUATIONS

Laboratory tests for serum electrolytes, chemistry, and hematology will be assessed at each study visit. [Table 10-1](#) provides the values that will be summarized.

Table 10-1 Clinical Laboratory Parameters

Electrolyte Panel	Chemistry Panel	Hematology Panel
Sodium	Total bilirubin	Hemoglobin
Potassium	Alkaline phosphatase	Hematocrit
Bicarbonate	Alanine aminotransferase	Red blood cell count
Chloride	Aspartate aminotransferase	White blood cell count
	Urea nitrogen	Platelet count
	Creatinine	Erythrocytes Mean Corpuscular Volume
	Calcium	
	Albumin	

Descriptive statistics for each clinical laboratory parameters (hematology, serum chemistry and electrolytes) will be presented by treatment group at baseline, each post-baseline assessment, and End of Study visits for raw data and change from respective baseline. Additionally, summary statistics will be presented for the change in each parameter from the baseline visit for Treatment Period 1 to the Baseline Visit for Treatment Period 2.

Post-baseline abnormal values, as defined by the normal limits, for hematology, serum chemistry, and electrolyte parameters will be summarized as shift tables from baseline to each post-baseline assessment and End of Study visits.

Tables will contain the number and percentage of subjects by treatment received at the time of measurement with post-baseline categories (low, high, and normal for hematology, chemistry, and electrolytes) compared to the respective baseline category for each parameter.

If data from both the central lab and a local lab is available for a given lab result, then the central lab value will be used in the analyses. If data is only available from a local lab for a given lab result, then local lab results will be transformed to be consistent to the central lab results for the analyses.

If a value for a laboratory value is reported below the lower limit of quantification, half of the lower limit of quantification will be used for summary and analysis.

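### The laboratory shift tables keep the later of two in-window results and omit out-of-window results, with no worst-value category, so they understate out-of-range values that are not reported as adverse events

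*SAP*

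**What the plan says.** Three rules in SAP 7 decide which laboratory values reach a table.

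- Unscheduled results: "Evaluations from Unscheduled Visits are to be mapped to Scheduled Visits to the extent possible per the protocol-specified windows".
- Surplus and out-of-window results: "Repeat or redundant observations within an assessment window and observations that do not fall within any predefined assessment window will be excluded from summaries".
- Repeats: the SAP's own example is a test repeated "such as to confirm an observed aberrant laboratory value, the analyses will use the later value if within the protocol-specified window".

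The windows come from Protocol 7 ("The allowable window for each study visit will be" ±3 days) and Protocol Table 3-1, which puts the follow-up visits at Days 42 and 84 in Period 1 and Days 133 and 175 in Period 2, each ±3 days.

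The protocol expects both kinds of result. Footnote a of Table 3-1 allows an unscheduled visit when site staff or the Investigator want to assess a subject's status, and requires the results to be entered in the eCRF: "This visit may require blood draws, vital signs, and/or review of concomitant medications". Protocol 15.6 adds: "The Investigator may repeat the diagnostic procedure or laboratory test or request additional tests to verify the results of the original tests".

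SAP 10.5 says that abnormal laboratory values "will be summarized as shift tables from baseline to each post-baseline assessment and End of Study visits". It gives no worst post-baseline or any-time category. SAP 12.4 leaves unreplaced text in force, so the same rules apply under the Contingent Parallel Design.

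**The concern.** A laboratory test is usually repeated because the first result was out of range. Keeping only the later result is therefore a selective rule: it can turn an abnormal entry into a normal one, and it seldom works the other way. An unscheduled blood draw is likewise most often taken because someone was worried about the subject, yet it enters a summary only if its date falls near a planned visit.

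The two rules act differently. Replacement changes the count at a given visit. Exclusion leaves the count at that visit correct, but the abnormality between visits appears in no shift table. A reader who takes these tables as the record of treatment-emergent laboratory abnormality will see too few. No inferential safety testing is planned (Protocol 10.3.4, SAP 10), so the descriptive tables are what the reader has for comparing treatments on laboratory results.

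**Working it through.** The documents give no figure for this point, so there is none to reproduce. Two checks of scale follow.

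**1. Days with a follow-up visit to map to.** Inputs: visit days and ±3-day windows from Protocol Table 3-1.

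- Period 1, Days 2 to 87: 86 days. The windows are Days 39–45 and 81–87, so 7 + 7 = 14 days are covered. 14/86 = 16%, leaving 84% in no follow-up window.
- Stopping at Day 84: 83 days, 7 + 4 = 11 covered, leaving 87% uncovered.
- Period 2, Days 93 to 178 and 93 to 175: the same counts, 14 of 86 and 11 of 83.
- The first follow-up window opens on Day 42 − 3 = Day 39. The sample schedule in Protocol Table 6-1 ends its escalation on Day 28. On that schedule, an unscheduled Period 1 result during escalation has no follow-up visit to map to.

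These are shares of calendar days. Scheduled samples are planned for the windows, so the share of data lost is smaller and is not known.

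**2. What an in-window repeat does to a high value.** Assumptions, none of them from the documents: the first and repeat values are bivariate normal, the upper limit of normal (ULN) is at the 97.5th percentile (z = 1.96), and the test-retest correlation ρ is 0.5 to 0.8.

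P(repeat > ULN | first > ULN) = P(both > ULN) / 0.025

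| ρ | P(both > ULN) | Still high | Would read normal |
|---|---|---|---|
| 0.5 | 0.00462 | 0.185 | 81.5% |
| 0.6 | 0.00622 | 0.249 | 75.1% |
| 0.7 | 0.00827 | 0.331 | 66.9% |
| 0.8 | 0.01097 | 0.439 | 56.1% |

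The last column applies only to high values that are repeated inside the window. If a fraction f of high values is so repeated, the share leaving the table is f × (56.1% to 81.5%): about 6% to 8% for f = 10%, and 17% to 24% for f = 30%. The documents do not give f. It is limited by timing: after a visit on its nominal day, only 3 days of the window remain (at most 6 if the visit was at the start of its window). A later repeat leaves the first value in place.

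**3. Effect on a comparison between treatments.** Take ρ = 0.7, and the extreme case in which every high value is repeated in-window. Without a shift, 2.50% of first values are high and 0.83% remain high. With an upward shift of 0.5 SD, 7.21% are high and 3.10% remain. The difference falls from 7.21 − 2.50 = 4.7 points to 3.10 − 0.83 = 2.3 points. The proportional loss is smaller in the shifted group (57% against 67%), and the ratio rises from 2.9 to 3.7. The absolute excess is understated; the ratio is not.

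**The case against.** The strongest reply is the adverse-event route. Protocol 3.3.2.5 requires the Investigator to assess every out-of-range laboratory result, and clinically significant ones are reported as adverse events and followed. The adverse-event tables have no visit-window filter, and an unblinded DSMC monitors safety (Protocol 10.7). This stands, and it limits the point. A reader might infer that the values most likely to show harm disappear, but the documents do not support that. What is lost from the tables is out-of-range values not judged significant, and the size of the excursion.

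Four other objections also stand in whole or part.

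- **ECG.** A reader might extend the point to the ECG abnormality summary. SAP 10.7 averages same-day ECGs, describes a summary by subject and type of abnormality without saying that it is by visit, and the unscheduled-visit footnote does not name ECG. Loss there is possible under the general rule but is not shown.
- **Contradiction.** SAP 7 may seem to exclude repeats and use them at once. An ordinary reading reconciles the sentences: one value per window, and the later one is kept. That reading still drops the first value.
- **Listings.** The exclusion is from summaries, not from the database. Protocol 10.6 promises listings, and the SAP's lists of tables and listings are not in the available text, so a worst-value table cannot be ruled out. A listing, however, is not a comparison of treatments.
- **Wording.** SAP 7 maps unscheduled results to visits as far as possible, which may allow some latitude. It still ties the mapping to the windows.

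**Conclusion.** The point holds for the laboratory shift tables. As written, SAP 7 and SAP 10.5 together shift visit counts towards normal when an abnormal value is repeated in-window, and leave abnormalities between visits out of the shift tables. The direction follows from the text; the size does not. The 84% of days outside a follow-up window is not 84% of data, and the 56% to 81.5% is not a general loss rate: it is conditional on an in-window repeat and rests on an assumed distribution and correlation. It would also be wrong to infer that the higher-risk treatment loses proportionally more; under the same model it loses more in absolute terms and less in proportion.

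The conclusion assumes that no worst-value table is specified in the parts of the SAP not available here. No efficacy conclusion depends on it. It is worth correcting because the data are already collected and the change is small.

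**What to change.** - **SAP 10.5:** add to the laboratory shift and abnormality tables a worst post-baseline value per treatment period, separately for low and high, drawn from scheduled, unscheduled, repeat and Early Termination results. State the period limits, for instance from the first randomised dose of the period, with washout results attributed as SAP 7 already provides.
- **SAP 7:** restrict the window rule to by-visit descriptive statistics, and limit use of the later value to samples declared technically invalid.
- **SAP 10.7:** clarification only. State that the treatment-emergent ECG abnormality summary counts all post-baseline readings, and reconcile same-day averaging with the later-value rule in SAP 7.
- **SAP 12.4:** confirm that the same rules apply to the single period of the Contingent Parallel Design.

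The cost is SAP wording and one derived record per parameter, direction and period. No new data are needed and conduct does not change. Abnormality counts will be somewhat higher and will include some isolated excursions that a repeat did not confirm; the by-visit tables remain alongside to put these in context.
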